The primary outcome of the study is to determine differences in glycemic control as measured by mean daily blood glucose concentration between treatment groups. For each subject, we will take the average of all pre-meal and bedtime glucose values collected after the first day of therapy during the hospital stay (up to 10 days).

Secondary outcomes include differences between treatment groups in any of the following measures:

1. Differences in mean daily glucose in patients admitted to medicine and surgery services.
2. Differences in mean daily glucose in patients with admission HbA1c lower than and higher than 8%.
3. Differences in mean daily glucose in patients with length of stay shorter and longer than 3 and 5 days.
4. Proportion of BG readings within target of 80 mg/dl and 180 mg/dl before meals.
5. Number of BG readings between 80 mg/dl and 180 mg/dl before meals without hypoglycemia.
6. Number of patients with hypoglycemia (defined as a BG < 70 mg/dl) and number of events adjusted by length of stay (event rate).
7. Number of patients with severe hypoglycemia (defined as a BG < 40 mg/dl) and number of events adjusted by length of stay (event rate).
8. Length of hospital stay.
9. Cardiac complications are defined as myocardial infarction, cardiac arrhythmia requiring medical treatment, or cardiac arrest.
10. Acute renal failure defined as a clinical diagnosis with documented new-onset abnormal renal function (increment in serum creatinine > 0.5 mg/dL from baseline).
11. Hospital mortality.

IV.d. Plan. This study will include male or female subjects > 18 years. Due to the design of this study, there will be no run-in period. Upon arrival to the emergency department or medical or general surgical wards, subjects will be screened. Patients with a known history of T2D treated with diet alone, any combination of OADs, and insulin prior to admission will be considered potential candidates for this study. Patients treated with degludec, glargine U300 or with long-acting GLP1-RA (dulaglutide, albiglutide and weekly exenatide) prior to admission will be excluded. Patients admitted with acute or chronic medical illnesses, emergency or elective surgical procedures and trauma would be included in the study. The goal of insulin therapy is to maintain fasting and pre-meal blood glucose levels between 80 mg/dl and 180 mg/dL while avoiding hypoglycemia.

A total of 180 patients with T2D with a blood glucose > 140 mg/dL and < 400 mg/dL will be randomized to receive:

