events, number of severe hyperglycemia, mean daily fasting BG, daily insulin dose, length of hospital stay, acute renal failure and hospital mortality. Blood glucose will be measured before each meal and at bedtime. For discrete outcomes (such as hypoglycemia outcomes), if the outcome is binary (e.g. with or without hypoglycemia), we will first conduct nonparametric comparisons based on a two-sided Chi-square test (or Fisher's exact test in the presence of low incidence rates), followed by the Cochran-Mantel-Haenszel test, which adjusts for the potential center effect. If the discrete outcome is a count outcome (such as the number of hypoglycemic event), we will perform Poisson regression (or Negative Binomial regression) that adjusts for the length of hospital stay to assess the difference in the count outcome between the treatment groups. We also value the repeated measures analyses based on mixed effect models. This is because they will allow us to assess treatment effect fine tuned according to other confounders of the BG outcomes. By these considerations, we will conduct both types of analyses to provide a thorough evaluation of the hypothesis of interest. For continuous outcomes that are not repeated measures (such as length of hospital stay), we will use two-sample t-tests or nonparametric Wilcoxon tests to compare them between groups. Transformations will be applied if normality violation is detected. Multivariate linear regression will be further conducted to assess the difference in continuous secondary outcomes between the two groups while other relevant covariates. We will use standard model selection and model checking procedures for linear regression to decide the final models and assess their fits to the data.

IV.f. Data and Safety Monitoring Board (DSMB):

The Data and Safety Monitoring Board (DSMB) will review unblended data on safety, treatment compliance, and evaluate the efficacy of the intervention being studied in this clinical trial. The DSMB will meet at 6-month intervals and report on study progress to the IRB.

IV.g. Interim Analysis and Stopping Rules: We plan to perform one interim analysis on the primary endpoint every 6 months and when half of the subjects have been randomized. The trial will be stopped if there is evidence beyond a reasonable doubt of a difference in the rate of death and hospital complications (two-sided alpha level, <0.01) between the treatment groups.

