GLP1-RA. GLP1-RA treatment is considered background medication (non-investigational medicinal product) and will not be provided during the trial. No dose adjustment or up-titration will occur during the trial.

SGLT2-i. The use of SGLT2-I is considered background medication (non-investigational medicinal product) and will not be provided during the trial. No dose adjustment or up-titration will occur during the trial.

V.c. Hospital Diabetes Education. Prior to discharge, participants will be trained in:

1. Diabetes education if not received within 1 year of admission
2. Recommended targets for fasting and premeal blood glucose between 90 to 130 mg/dL
3. Use of glucose meters for home glucose self-monitoring
4. Keeping BG records, and will receive a logbook to record glucose tests results.
5. Hypoglycemia prevention, recognition and management
6. Insulin administration

V.d. Follow-up Care:

- Provide glargine insulin 1-month supply at each clinic visit.
- A member of the diabetes research team will contact patients via telephone call every 2 weeks for a total of 3 months.
- Patients will be asked to attend outpatient visits at 1 and 3 month after hospital discharge.
- Recommendation on insulin adjustment to be provided after each telephone contact and/or clinic visit by a licensed physician (fellow or study physician) (section V.f).

V.e. During follow up we will collect the following information:

1. Glycemic control:
 - a. Mean daily fasting and premeal blood glucose levels
 - b. HbA1C at 1 and 3 months after hospital discharge
 - c. Hypoglycemic events (BG < 70 mg/dl and < 40 mg/dl)
 - d. Hyperglycemic events (BG > 240 mg/dl)
2. Diabetes treatment:
 - a. Insulin dosage (unit/day)
 - b. Use of oral agents

- c. Protocol adherence
- 3. Clinical Outcome:
 - a. Hospital readmissions
 - b. Emergency room visits
 - c. Postoperative complications

V.f. Primary care physicians will be provided with the following algorithm for outpatient basal insulin dose adjustment every 2 weeks:

Basal Insulin (glargine U300 and glargine U100)	
If mean FBG > 180 mg/dL for the last 3 consecutive days and no hypoglycemia or no random BG (RBG) <70 mg/dL	Increase daily dose by 4 IU
If mean FBG > 140 mg/dL for the last 3 consecutive days and no hypoglycemia < or no RBG <70 mg/dL	Increase daily dose by 2 IU
If mean FBG between 100 - 140 mg/dL and no hypoglycemia or no RBG <70 mg/dL	No Change
If any FBG between 70 – 99 mg/dl	Decrease by 4 IU or 10% of total daily dose

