If any FBG or RBG 40- 69 mg/dl	Decrease by 8 IU or 20% of total daily dose
If any FBG or RBG < 40 mg/dl	Decrease total daily dose by 30 - 40%

V.g. Aim 2. Statistical Analysis:

V.g.1. Sample Size and Power Calculations: The primary endpoint in Aim 2 is difference in glycemic control (mean daily BG) after hospital discharge. Under the same assumptions for equivalence margin and BG variability as in Aim 1, we have the same sample size requirement (i.e. 78 subjects per group after 10% attrition). Accounting for 10% attrition rate, we would need 90 patients per treatment group (total # of patients to be recruited: 180 subjects, 90 per treatment group), to achieve >80% power.

V.g.2. Analysis of Primary Endpoint:

The primary endpoint in this study is glycemic control measured by mean daily BG concentration after hospital discharge. Secondary outcomes include rate of hypoglycemia during follow-up, change in HbA1c, body weight in kilograms, number of episodes of severe hyperglycemia, complications and emergency room visits or hospital readmissions at 12 weeks post-discharge. To analyze these outcomes, we will follow the same analytic strategy proposed for the secondary endpoints of Aim 1. We will first compare the primary outcome using two-sample t-tests (or Wilcoxon tests) or one-way ANOVA, followed by multivariate linear regression to estimate and test the difference between the two treatment groups while simultaneously accounting for other potential confounders. Transformations will be applied if normality violation is detected. Stepwise, backward, or forward model selection strategy will be adopted to determine the variables to be included in the final model. Standard diagnostic and model checking procedures will be applied to examine the fit of the developed models.

DATA HANDLING AND RECORD KEEPING:

Data collection records with personal identifiers will be stored in locked file cabinets. Presentation of the study results at regional or scientific meetings or in publications will not identify subjects. Access to research and confidential records will be limited to clinical investigators, research coordinators, and the IRB at Emory University.

All data will be entered electronically in Redcap by participating sites. Sponsor site expects data to be entered in Redcap within 10 days of phone call or outpatient visit.

VI. Methods and Procedures Applied to Human Subjects:

VI.a. Subject Population:

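### Aim 2 event counts after discharge inherit a model that adjusts for length of hospital stay, and the post-discharge time at risk is not in it

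*Combined protocol and SAP*

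**What the plan says.** Section V.g.2 (Aim 2) opens its list with "Secondary outcomes include rate of hypoglycemia during follow-up" and goes on to include "number of episodes of severe hyperglycemia" and "emergency room visits or hospital readmissions at 12 weeks post-discharge". It then states "To analyze these outcomes, we will follow the same analytic strategy proposed for the secondary endpoints of Aim 1". The rest of V.g.2 deals with the continuous primary outcome.

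The strategy referred to is in IV.g, Analysis of Secondary Endpoints (Aim 1). Binary outcomes go to chi-square or Fisher's exact test and then Cochran-Mantel-Haenszel. For counts the text is "we will perform Poisson regression (or Negative Binomial regression) that adjusts for the length of hospital stay". Section IV.c shows what that adjustment is for, since it describes the Aim 1 hypoglycemia outcomes as "number of events adjusted by length of stay (event rate"). Stay is the denominator of a rate.

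Aim 2 data are collected after discharge. Section V.d says "A member of the diabetes research team will contact patients via telephone call every 2 weeks for a total of 3 months", with clinic visits at 1 and 3 months. Section V.e lists "Hypoglycemic events (BG < 70 mg/dl and < 40 mg/dl") among the items collected. The outpatient flow chart runs from week 0 to week 12.

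**The concern.** In Aim 1, length of stay is a sensible exposure, because inpatient events occur during the stay. Carried into Aim 2 it no longer measures exposure. The index admission is over before the first Aim 2 event can be counted, so the stay and the period observed do not overlap.

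The exposure that matters is the number of days from discharge to week 12, withdrawal, death or last contact. No section names it. It will differ between patients: V.g.1 plans for 10% attrition, and VI.d lets subjects leave at any time or be withdrawn for safety or non-compliance.

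Fewer hypoglycemic episodes on U300 after discharge is part of the Aim 2 hypothesis in the Specific Aims. If those episodes are analysed as counts, the rule as written governs a comparison the trial intends to interpret. The trial is open label, and a choice of exposure made after the data are seen would be hard to defend.

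**Working it through.** **The plan's own figure.** The documents give no figure for the post-discharge count analysis. The only Aim 2 calculation, in V.g.1, is for mean daily glucose: margin 18 mg/dl, SD 45 mg/dl, true difference 0, one-sided test, 80% power. Alpha is not stated. At an assumed one-sided 0.05, 2 × [45 × (1.645 + 0.842) / 18]² = 77.3, which rounds up to the stated 78 per group. This point does not touch that figure.

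**One patient.** Follow-up is 12 weeks × 7 = 84 days. Two outpatient events give 2/84 = 0.024 per day, whatever the stay. Divided by stay, the same two events give 2/2 = 1.0 per day after a 2-day stay, 2/4 = 0.5 after 4 days and 2/10 = 0.2 after 10 days. The five-fold spread reflects time in hospital only.

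**Stay as offset, no true effect.** The expected rate ratio is 1 / (U300 stay ÷ U100 stay):
- stays 10% longer on U300 (assumed): 1/1.1 = 0.91
- stays 20% longer (assumed): 1/1.2 = 0.83
- equal stays: 1.00

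**Stay as covariate only.** Stay then adds little, but follow-up is uncorrected. With assumed dropout of 15% on one arm and 5% on the other, each at mid-follow-up, the ratio under no effect is (1 − 0.15 × 0.5) / (1 − 0.05 × 0.5) = 0.925/0.975 = 0.949, a bias of about 5%.

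**Simulation.** These inputs are assumptions, not figures from the documents:
- 80 patients per arm, 1,500 runs
- stay lognormal, median 4 days, log-SD 0.5, limited to 1 to 10 days
- 20% early dropout, uniform over days 7 to 84, unless varied
- mean 0.55 events per 84 days, negative binomial dispersion 2

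Under full follow-up this gives 1 − (1 + 2 × 0.55)^(−0.5) = 31% of patients with at least one event. The documents expect about 20% (X.a) and report about 30% in the earlier discharge study for oral agents plus basal insulin (section II). The model was negative binomial regression with the dispersion known. Cells show the mean rate ratio, with the percentage of two-sided 5% tests that rejected.

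| Scenario | Stay as offset | Follow-up days as offset | Stay as covariate |
|---|---|---|---|
| No effect, equal stays | 0.985 (4.4%) | 0.991 (6.1%) | 0.990 (6.1%) |
| No effect, U300 stays × 1.25 | 0.803 (10.7%) | 0.990 (5.1%) | 0.990 (5.3%) |
| No effect, U300 stays × 0.8 | 1.241 (9.3%) | 0.990 (5.1%) | 0.989 (5.1%) |
| No effect, dropout 30% U300, 10% U100 | 0.900 (5.5%) | 0.998 (4.7%) | 0.903 (6.7%) |
| True ratio 0.60, equal stays | 0.584 (26.7%) | 0.600 (30.5%) | 0.601 (31.1%) |
| True ratio 0.60, U300 stays × 0.8 | 0.728 (12.6%) | 0.599 (32.8%) | 0.597 (31.5%) |

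The shifts agree with the formula (1/1.25 = 0.80; 1/0.8 = 1.25). The dropout row can be checked by hand. Mean follow-up of a dropout is (7 + 84)/2 = 45.5 days, so the exposure ratio is (0.7 × 84 + 0.3 × 45.5) / (0.9 × 84 + 0.1 × 45.5) = 72.45/80.15 = 0.90.

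With equal stays and no effect, the SD of the log rate ratio is 0.365 with the stay offset and 0.329 with the follow-up offset. The information retained is (0.329/0.365)² = 0.81, so about 19% is lost with no bias.

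**The case against.** Four points can be made for the plan.

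- **Hypoglycemia may never reach the count model.** The protocol often uses rate for the percentage of patients: 3% and 12% in the opening background, about 30% in section II, restated as an incidence in V.a. On that usage Aim 2 hypoglycemia goes to chi-square, Fisher or Cochran-Mantel-Haenszel, and stay does not enter. This stands as an ambiguity. The Aim 2 hypothesis speaks of number and V.e collects events, so a count reading is equally open. Severe hyperglycemia is worded as a count in any case.
- **The cross-reference may mean only that test family is matched to outcome type,** with follow-up time substituted for stay. That is a natural adaptation and may be what was intended, but the text does not say it.
- **The model adjusts for stay; the word offset is not used.** This is correct. The offset reading comes from the event-rate wording in IV.c, so both readings are worked above.
- **The arms are randomized and nothing predicts unequal stays or dropout.** This also stands, so no direction of bias can be claimed. But stay is itself a post-randomization outcome (IV.c, item 8), and equality cannot be assumed.

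A reader might also infer that outpatient rates would be overstated at least eight-fold, from 84 days over a 10-day stay. The documents do not support this. The 10-day limit in IV.c applies to glucose readings averaged for the primary outcome, and the count model puts no cap on stay. An inflation common to both arms would in any case cancel in the rate ratio.

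**Conclusion.** The point holds for Aim 2 outcomes analysed as counts: severe hyperglycemia episodes certainly, and hypoglycemia if events are counted. Followed literally, the rule brings in an exposure that contains none of the observed period and omits the one that does. Both readings of the adjustment leave something wrong. An offset loses precision with equal stays and misstates the ratio with unequal ones; a covariate leaves unequal follow-up uncorrected.

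The size is conditional. The ratios of 0.91 and 0.83 need the offset reading and stays assumed 10% or 20% longer on U300. The 5% figure needs the covariate reading and assumed dropout of 15% against 5%. The precision loss rests on the simulation's assumed spread of stays and event rates.

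It would go too far to conclude that the outpatient hypoglycemia comparison is bound to be biased, or that it favours either arm. With equal stays and equal follow-up, neither reading shows material bias. Only secondary outcomes are affected; the Aim 2 primary analysis, its sample size and the binary analyses are not. The correction should be made before the data are analysed.

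**What to change.** In V.g.2, replace the cross-reference for event outcomes with wording such as:

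> Post-discharge event counts will be analysed by Poisson or negative binomial regression with the log of days from discharge to last contact (maximum 12 weeks) as offset, in place of length of hospital stay; the proportion of patients with at least one event will be compared by the binary methods of Aim 1.

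This keeps the plan's choice between Poisson and negative binomial, which needs no change here. The text should also say whether the Aim 2 hypoglycemia outcome is the proportion of patients, the number of events, or both.

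The cost is one or two sentences. Sample size and visit schedule do not change. The scheduled calls and visits, entered in Redcap, should already generate the dates needed. No section lists discharge date and last-contact date as data items, so the sponsor should confirm that the case report form holds them.

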- If a patient develops hypoglycemia (BG <70 mg/dL), the insulin TDD (basal and prandial) should be decreased by 20%.
- If a patient develops severe hypoglycemia (BG <40 mg/dL), the insulin TDD (basal and prandial) should be decreased by 30-40%.

IV.g. Data Analysis:

Aim 1. To determine differences in inpatient glycemic control, as measured by mean daily blood glucose concentration and frequency of hypoglycemia, in general medicine and surgery patients with T2D treated with basal bolus regimen with glargine U300 and U100 plus glulisine insulin before meals.

Due to the lack of efficacy and safety data with the use of glargine U300 in the inpatient setting, periodic conduct interim analyses will be conducted every 6 months to monitor the primary outcome and rate of hypoglycemia, and to modify the study design regarding interval of administration and dosage adjustment for basal insulin (see page 9, Data Safety Monitoring Plan, sections IV. f. and IV.g.).

Sample Size and Power Calculations:

The primary endpoint in this study is glycemic control measured by mean daily BG concentration. To show the non-inferiority of glargine U300 and U100 in terms of glycemic control, we set the equivalence margin as 18 mg/dl (1 mosm/l), from a view that a difference <18 mg/dl is usually not considered as clinically significant (12, 14, 16). Based on the results from Rabbit medicine and surgery trials, it is reasonable to assume the standard deviation of mean daily BG is bounded above by 45 mg/dl. Assuming the true BG difference between the treatment groups is zero, and using one-sided, two-sample t-tests, we require 78 subjects for each treatment group to achieve 80% power. Accounting for 10% attrition rate, we would need 90 patients per treatment group, which means 180 subjects in total, to achieve >80% power in Aim 1.

Analysis of Primary Endpoint:

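### The Aim 2 primary endpoint may be transformed if it looks non-normal, although its non-inferiority margin is an absolute 18 mg/dl and no converted margin or back-transformation is given

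*Combined protocol and SAP*

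**What the plan says.** Section IV.g (Sample Size and Power Calculations) fixes the margin in glucose units: "we set the equivalence margin as 18 mg/dl (1 mosm/l". The reason given is also an absolute difference: "a difference <18 mg/dl is usually not considered as clinically significant". The SD is on the same scale ("it is reasonable to assume the standard deviation of mean daily BG is bounded above by 45 mg/dl"). The calculation is made "using one-sided, two-sample t-tests", and its result is "we require 78 subjects for each treatment group to achieve 80% power".

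Section V.g.1 takes this over for Aim 2: "Under the same assumptions for equivalence margin and BG variability as in Aim 1".

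Section V.g.2, headed as the analysis of the primary endpoint, names mean daily glucose after discharge. It compares the primary outcome by t-test, Wilcoxon test or one-way ANOVA, and then by multivariable linear regression. The next sentence is "Transformations will be applied if normality violation is detected". The plan does not name the transformation, the trigger, a margin on the transformed scale or a route back to mg/dl. V.g.2 does not mention 18 mg/dl.

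The primary analysis of Aim 1 (IV.g) has no transformation sentence. The matching sentence there belongs to the secondary endpoints, so this point concerns Aim 2 only.

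**The concern.** A margin and the estimate set against it must be on the same scale. The plan's margin, SD and sample size all refer to a difference in arithmetic means in mg/dl. A non-linear transformation changes the quantity estimated: the log gives a ratio of geometric means, and other transformations give contrasts with no natural unit. Whether this happens would depend on a look at the data in an open-label trial, and someone would then have to choose a converted margin after the fact.

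The two scales can also disagree on substance. Geometric means give less weight to high glucose values. An arm with relatively more spread therefore looks better on the log scale than its mean in mg/dl would show, and an arm with less spread looks worse. The Aim 2 primary conclusion could depend on which scale was used.

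**Working it through.** **Inputs from the plan.** Margin 18 mg/dl, SD 45 mg/dl (an upper bound), true difference zero, one-sided t-test, 80% power, 78 per group (IV.g, carried to V.g.1); 90 per group recruited with 10% attrition. For illustration only: means and SDs of 145±32 and 172±47 mg/dl, the inpatient results of the Rabbit-Surgery trial (section III).

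**Assumptions.** One-sided 5% (the plan states no level); lognormal or gamma patient means; log transformation; margin converted as ln((control mean + 18)/control mean). The plan specifies none of these.

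**1. The plan's own figure.** n = 2 × [SD × (z0.95 + z0.80)/margin]² = 2 × [45 × (1.645 + 0.842)/18]² = 77.3, so 78 per group, as stated. Exact t-test power at 78 is 80.0%. One-sided 2.5% would give 99, so 5% is the level that fits. With 90 recruited, 90 × 0.9 = 81 are evaluable, and raw-scale power is 81.3%.

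**2. The margin as a ratio.** (145 + 18)/145 = 1.124; (172 + 18)/172 = 1.105. Conversely, a ratio fixed at 1.124 would allow 172 × 18/145 = 21.4 mg/dl at a control mean of 172.

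**3. False non-inferiority at a true difference of exactly 18 mg/dl.** U300 mean 163, U100 mean 145, 78 per arm, at least 20,000 simulated trials per scenario. Non-inferiority is declared if the upper 95% one-sided limit is below the margin. For lognormal data the geometric mean is mean/√(1 + CV²), where CV = SD/mean. The log-scale margin is a ratio of 1.124.

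| SD U300 / U100 | CV U300 / U100 | True geometric mean ratio | Log scale | Raw scale |
|---|---|---|---|---|
| 36 / 32 (equal CV) | 22.1% / 22.1% | 1.124 | about 5% | about 5% |
| 45 / 45 | 27.6% / 31.0% | 157.1/138.5 = 1.135 | about 3% | about 5% |
| 32 / 45 | 19.6% / 31.0% | 160.0/138.5 = 1.155 | about 1% | about 4.5% |
| 47 / 32 | 28.8% / 22.1% | 156.6/141.6 = 1.106 | 10-11% | 5.1-5.5% |

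The geometric mean ratio explains the pattern. The log test is anti-conservative only where the true ratio is below 1.124, and that requires the larger CV in U300. Converting the margin at the observed instead of the true control mean still gives about 10% in the last row. The raw-scale limit stays at about 4-5.5% in all four rows.

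**4. Power with no true difference.** At 81 per arm and SD 45 in both arms, log-scale power is about 79-80% (lognormal) or 75-77% (gamma), against 81% raw. At SD 32, it is about 95-97% on the log scale and 97% raw.

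**The case against.** The strongest reply is that these error rates belong to a procedure the plan does not contain. V.g.2 names no log transformation, no margin conversion and no normality test, and it never says that a limit is compared with 18 mg/dl on any scale. This stands. The missing decision rule is the larger gap, and the present point can be merged with it. It does not disappear once that rule is added, because the transformation sentence would still be in force.

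The scope can also be questioned. The paragraph lists secondary outcomes as well, and the sentence may be text carried over from the secondary analyses of Aim 1, or may concern only the regression step. Its position directly after the tests of the primary outcome makes coverage of the primary endpoint the more natural reading, but not the only one.

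A reader might infer more than the documents support:

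- *That transformation inflates false non-inferiority in general.* It does not. With equal CVs there is no inflation, and with equal SDs the log test is conservative. The SDs of 47 and 32 come from sliding-scale and basal-bolus inpatient arms. Nothing in the plan suggests that U300 is the more variable arm.
- *That a transformation is almost sure to be triggered.* Under assumed skewed shapes, a 5% Shapiro-Wilk test would reject normality in about 69-98% of trials at SD 45 and 42-82% at SD 32. The plan gives no outpatient distribution and does not name that test.
- *That the margin becomes unusable.* A transformed model can be back-transformed to a difference in mg/dl. The plan is silent on this, so the analysis is under-specified, not impossible.
- *That the trial is underpowered.* The loss is about 1 to 6 points at the upper-bound SD, and little is lost at SD 32.

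**Conclusion.** The scale mismatch is real and rests on no distributional assumption: a stated rule can move the Aim 2 primary comparison off the scale on which its margin and sample size are defined, and the plan offers no way back. The consequence is conditional on two things, detected non-normality and a non-linear transformation.

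If both occur with a log transformation, the error rate at the margin could lie anywhere from about 1% to about 11%, depending on which arm has the larger CV, under the assumptions listed (one-sided 5%, skewed patient means, margin converted at the control mean). The upper figure is an illustration and not a forecast.

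The transformation is also not needed to protect the error rate. At this sample size the untransformed limit held about 4-5.5% on the skewed data examined. The sentence should be changed because it affects a primary conclusion and costs almost nothing to correct.

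**What to change.** In V.g.2, restrict the transformation sentence to secondary outcomes and add text to this effect: *Mean daily blood glucose is analysed untransformed in mg/dl. The confidence limit for the U300 minus U100 difference in means is compared with 18 mg/dl. Transformed and Wilcoxon results are supportive only.* The Wilcoxon clause is needed because a rank test also gives no difference in means to set against the margin.

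Unequal-variance standard errors, and a bootstrap limit for the same mean difference as a sensitivity analysis, are reasonable options but not essential.

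The cost is one or two sentences. No data, patients or clinical procedures change, and the sample size stays at 78 per group (90 recruited). The downside is a slight loss of efficiency if the data prove strongly skewed. If the plan is also revised to state a margin-based decision rule, both changes can be made in the same sentence.
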